2.1. Background Information

The decline of cognitive functions, especially memory, is a common complaint, both during the normal ageing process and in dementia (1): More than half of the population will probably face such symptoms in their second half of life.

Parallel to cognition, sleep architecture changes in older age, including a reduction of slow wave sleep (for a review see (2)). Given the importance of sleep for the consolidation of memory (for a review see (3) and (4)) and its role in reducing cellular waste (including amyloid, the pathological hallmark of Alzheimer's disease) via the glymphatic system (5), it seems plausible that a deterioration of sleep in older individuals partly explains a worsening of memory functions.

Despite the importance of the problem, there is still a lack of effective measures against cognitive decline in ageing individuals.

However, advances in neuroscience within the last few years have given us an increasingly detailed understanding of the oscillations of brain activity in neural circuitries associated with cognitive processes, offering possibilities of influencing them.

Transcranial alternating current stimulation (tACS) is an established, safe way to non-invasively modulate oscillations in neuronal networks and thus potentially restore and improve the associated cognitive functions (for a

recent review of applying tACS to improve cognition in various contexts see (6), for tACS to improve memory in healthy adults see (7)).

2.2. Scientific Rationale

This controlled cross-over pilot study will be used to prepare for a full-scale RCT in patients with mild cognitive impairment by investigating feasibility as well as acceptability and adherence of the study procedures in a sample of n=28 healthy elderly adults. Any effect on memory performance and sleep EEG will be documented but is not a requirement for the development of an RCT. We include people over 50 years of age because memory problems and neurodegenerative diseases (specifically Alzheimer's Disease) occur in the second half of life. The exclusion criteria are designed to ensure that people are not cognitively impaired by a disease of the brain or other impairment of bodily functions. In addition, we exclude contraindications to tACS.

The pilot study serves as a basis for the application of the technique in specific patient groups, in particular those with mild cognitive impairment.

3. Specific Aims

3.1. Aim 1

To establish acceptability of cognitive testing during tACS in healthy elderly participants. The threshold is set to 80% of participants.

3.2. Aim 2

Evaluation of an effect of a single session of gamma-tACS on memory (a) and associative memory (b) performance compared with control tACS. The estimand of interest is the comparison of the individual results of the memory tests at the individual and at the group level (paired t-test or a non-parametric test, respectively), for delayed (immediately after stimulation) and ultra-delayed recall (after a night of sleep as well as after 5 days).

3.3. Aim 3

Feasibility (a) and acceptability (b) of an ambulatory single-channel EEG device. The estimands of interest are the proportion of participants with at least four hours of recording in the first night (a) and the proportion of participants with three nights of at least 4 hours of EEG data (b).

3.4. Aim 4

The comparison of specific sleep EEG features, i.e. sleep spindles (a) and slow wave sleep (b), which are both prominently associated with cognitive functioning, especially memory processes, after each stimulation condition. Comparison will be on individual and on group level (via t-test or a non-parametric test, respectively).

3.5. Aim 5

To investigate whether there is a correlation between the effects of tACS (versus control control tACS) on memory recall and memory-associated sleep EEG features (especially amount of sleep spindles and slow wave sleep) on an exploratory level.

3.6. Aim 6

To investigate the effect of a single session of gamma-tACS (compared to control control tACS) on different cognitive functions, i.e. a letter fluency task (a), executive functioning (Stroop Test (b), Trail Making Test (c)) and attention (Attentional Performance, TAP (d)). These tests will be performed during stimulation and on the day after stimulation, and comparison will be calculated on the individual and on the group level (paired t-test or non-parametric test, respectively). For (a) the number of correct words, of perseverations and of rule breaks will be calculated. For (b) and (c) time for test completion and errors will be calculated. For (d) percentile ranks for the following subtests will be calculated: Alertness, Go/NoGo, Divided Attention, Visual Scanning.

3.7 Aim 7

To investigate whether there is a correlation between the effects of stimulation (in general) and/or the specific type of stimulation (gamma versus control) on the motor activity level measured by an actigraphy watch.

3.8 Aim 8

To investigate if there is a relationship between the brain excitability derived from the subjective effect of tACS and the motor threshold measured by TMS.

Specific Aims with Measures and Aim-Specific Statistical Analysis Plans

| Specific Aim | Outcomes Measures | Population Parameters to be Estimated ("Estimands") | Statistical Estimators |
|--|---|--|--|
| Aim 1: To investigate the feasibility of cognitive testing during tACS | Fraction of participants who complete both stimulation and cognitive testing sessions | Proportion of participants with completed stimulation- and testing-protocol | Observed proportion and 95% C.I. |
| Aim 2: Evaluate the effect of gamma-tACS on memory testing | Results of delayed ultra-delayed verbal memory and associative verbal memory recall (after stimulation, day after stimulation and 5 days after stimulation) for gamma versus control tACS | Memory recall in Rey Auditory Verbal Learning Test (a) and a word association test (b); amount of words and word-pairs remembered after stimulation, on day after stimulation and 5 days later will be recorded | Comparison between results after stimulation and sham on individual and group level (mean differences, regression coefficients, components of variance) |
| Aim 3: Investigate feasibility (a) and acceptability (b) of wearable device (single-channel EEG during the night) | Fraction of participants wearing the device on (a) the first and (b) all three nights planned according to the protocol. | Proportion of participants having worn the device during (a) the first and (b) all three nights for at least four hours each night | Observed proportion and 95% C.I. |
| Aim 4: Evaluate the effect of gamma-tACS on sleep spindles (a) and slow wave sleep (b) compared to sham stimulation | Amount of sleep spindles (a) and slow wave sleep (b) after tACS-stimulation and control stimulation. | Differences (individual level and means) of sleep spindle frequency (maximum number per hour) and slow wave activity (maximum minutes of slow wave sleep per hour) | Comparison between results after gamma-tACS and control tACS on individual and group level (mean differences, components of variance, regression coefficients) |
| Aim 5: To investigate whether there is a correlation between memory recall and sleep EEG | Memory and associative memory recall performance; EEG features (as for aim 4) | Correlation between changes in memory recall and sleep EEG (amount of spindles and slow wave sleep) for gamma- versus control tACS | Exploratory investigation of correlations (Pearson's) between stimulation induced changes in memory recall performance and sleep EEG features |
| Aim 6: To investigate the effect of stimulation on different cognitive functions, i.e. a letter fluency task (a), executive functioning (Stroop Test (b), Trail Making Test (c)) and attention | Effect of tACS and control stimulation on cognitive testing during and on the day after stimulation. | For (a) the number of correct words, of perseverations and of rule breaks will be calculated. For (b) and (c) time for test completion and errors will be calculated. For (d) percentile ranks for the following subtests will be calculated: Alertness, Go/NoGo, Divided Attention, Visual Scanning | Comparison between results after stimulation and sham on individual and group level (mean differences, regression coefficients, components of variance) |

| (Attentional Performance, TAP (d)) | | | |
|--|--|--|---|
| Aim 7: To investigate whether there is a correlation between motor activity level and stimulation | Effect of stimulation on motor activity level | Correlation between changes in the amount of motor activity the day after stimulation versus the day before; (a) after stimulation in general and (b) after gamma- versus control stimulation. | Exploratory investigation of correlations (Pearson's) between the day before and after the (respective) stimulations. |
| Aim 7: To investigate whether there is a correlation between the TMS motor threshold and the tolerated tACS amplitude (based on subjective symptoms) | Association between TMS motor threshold and symptoms from tACS | Correlation between the level of TMS motor threshold and the highest tolerated tACS level (21Hz and 40Hz, lower value). | Exploratory investigations of correlations (Pearson's) between the measures (% and mA). |

4. Study Design

This is a single-center prospective interventional pilot study with a controlled crossover-design. Each participant is exposed once to the intervention (tACS) and once to the control intervention (control tACS) to allow not only an interindividual but also an intraindividual comparison of outcomes under both conditions. Thus, each participant can serve as their own control.

First, an online prescreening (in REDCap) is performed, where basic eligibility information and informed consent for a screening by telephone is obtained. If, in the subsequent phone screen, inclusion/exclusion criteria are met and the participant provide verbal consent, a meeting on site (UNC Chapel Hill) will be arranged, where participants will sign informed consent and undergo baseline assessments (day 1). Afterwards, participants will receive the single-channel EEG for the following night (night 1). The next day (day 2), the intervention (gamma-tACS or control tACS) during cognitive testing will take place. During the following night (night 2) the EEG will be worn again for recording of sleep EEG at home. The follow-up cognitive testing will be scheduled for the day after (day 3), and again for the fifth day after stimulation (memory recall by telephone).

This procedure will be repeated for the respective other intervention (gamma-tACS or control tACS) one week (5-9 days) later. Each participant will be wearing an actigraph (accelerometer wristband) during the study period. Additionally, we will perform motor thresholding by TMS on day 2. Additionally, TMS motor thresholding will take place during day 2.

Centralized services are not used. All data (including baseline assessment, cognitive testing results) are stored in a REDCap database.

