| Specific Aims (objectives) | 
Aim 1: To establish acceptability of cognitive testing during tACS in healthy elderly participants.
 
Aim 2: To investigate the effect of a single session of gamma-tACS (compared to control tACS) on verbal memory (a) and associative memory (b) performance during stimulation, on the day after stimulation and after five days.
 
Aim 3: To establish feasibility of at-home use of a single-channel EEG device during one night (a) and acceptability during three nights (b).
 
Aim 4: To investigate the effect of a single session of gamma-tACS (compared to control tACS) on the amount of sleep spindles (a) and slow wave sleep (b) occurring during the night after the intervention.
 
Aim 5: To see if there is a correlation between memory recall performance and sleep EEG features (especially spindles, slow waves).
 
Aim 6: To investigate the effect of a single session of gamma-tACS (compared to control tACS) on a letter fluency task (a), executive functioning (Stroop Test (b), Trail Making Test (c)) and attention (Attentional Performance, TAP (d)).
 
Aim 7: To see if the motor activity pattern (measured by actigraphy) changes after stimulation/type of stimulation.
 
Aim 8: To investigate if there is a relationship between the brain excitability derived from the subjective effect of tACS and the motor threshold measured by TMS.
 |
| Target Population | 
Inclusion Criteria
 
 • >50 years old 
Exclusion Criteria
 
 • Implanted device or metal in head (including cochlear implant or other hearing aid), cardiac pacemaker or any other powered medical device • Known neurological disease from history (epilepsy, sleep disorder (insomnia, sleep apnea, restless legs syndrome, |

| | |
|----------------------|--|

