| Numbers of Enrollees | This pilot study requires n = 28 participants who complete all aspects of the protocol. Participants are recruited and enrolled until this target is reached. We anticipate screening up to 100 participants and enrolling up to 50 participants. |

| | |
|--|---|
| Intervention | 
This is a single-center prospective interventional control controlled cross-over pilot study.
 
The intervention consists of the application of tACS stimulation in the gamma-frequency range during approximately one hour of cognitive testing.
 |
| Outcome Measures | 
Aim 1: Cognitive testing during tACS completed in >80% of participants.
 
Aim 2: Participants will memorize 15 words ("Rey Verbal Learning Test", (a)) and 8 word-pairs (associative verbal memory, (b)) during gamma-tACS and control tACS. They will be required to recall the words after a short delay on the same day, on the day after and after 5 days ("ultra-delayed recall"). The number of correctly remembered words (a) and word-pairs (b) will be recorded.
 
Aim 3: Feasibility (a) will be considered feasible if the device has been worn for at least 4 hours during the first night for >/= 80% of participants. Acceptability (b) will be considered as given if the device has been worn for at least 4 hours during each of the three nights in >/=80% of participants.
 
Aim 4: Amount of sleep spindles (a) and slow wave sleep (b) during sleep recording.
 
Aim 5: Exploration of correlation between memory recall performance and sleep EEG features (especially spindles, slow waves). Difference in recall scores (verum versus sham tACS) will be correlated with differences in sleep EEG features (verum versus sham tACS).
 
Aim 6: For (a) the number of correct words, of perseverations and of rule breaks will be calculated. For (b) and (c) time for test completion and errors will be calculated. For (d) percentile ranks for the following subtests will be calculated: Alertness, Go/NoGo, Divided Attention, Visual Scanning.
 
Aim 7: Exploration of correlation between amount of motor activity/inactivity phases (measured by actigraphy watch) and stimulation versus no stimulation as well as gamma- versus control stimulation.
 
Aim 8: Exploration of correlation between the TMS motor threshold and the maximal tolerated amplitude (according to the subjective symptoms) for tACS.
 |

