| Statistical Analysis Plans for Each Aim | 
Aim 1: Proportion (percentage and 95% confidence interval) of participants with completed cognitive testing during stimulation study session.
 
Aim 2: Comparison of memory and associative testing after stimulation and sham on individual and group level using ANCOVA.
 
Aim 3: Proportion (percentage, 95% confidence interval) of participants with at least four hours of EEG-data in the first night (a).Proportion (percentage,
 |

| | |
|-------------------------------|--|
| | 95% confidence interval) of participants who successfully collected at least four hours of EEG for all three study nights (b). Aim 4: Comparison of sleep spindles (a) and slow wave sleep (b) derived from sleep EEG for verum versus control tACS using ANCOVA. Aim 5: Exploratory investigation of correlations (Pearson's) between stimulation induced changes in memory recall performance and sleep EEG features. Aim 6: Comparison of test results after stimulation and sham on individual and group level using ANCOVA. Aim 7: Exploratory investigation of correlations (Pearson's) between changes in motor activity pattern before and after stimulation. Aim 8: Exploratory investigation of a correlation (Pearson's) between the level of the TMS motor threshold and the tolerated tACS level (lower level from 21 Hz and 40 Hz, based on subjective symptoms). |
| Study Duration | 1 year |
| Participation Duration | 2 weeks |
| Enrollment Duration | 6 months |

2. Introduction

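### Aim 7 asks whether motor activity changes after stimulation, but the analysis named, Pearson's r between days or between changes, cannot show a mean change

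*Combined protocol and SAP*

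**What the plan says.** The Synopsis words the aim as "To see if the motor activity pattern (measured by actigraphy) changes after stimulation/type of stimulation", and the outcome column of the Specific Aims table in Section 3 gives "Effect of stimulation on motor activity level". Both describe a change or an effect.

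Three places name a statistic for this aim, and each names Pearson's r:

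- Synopsis, Statistical Analysis Plans: "Exploratory investigation of correlations (Pearson's) between changes in motor activity pattern before and after stimulation".
- Specific Aims table, estimator column: "Exploratory investigation of correlations (Pearson's) between the day before and after the (respective) stimulations". The estimand column beside it reads "Correlation between changes in the amount of motor activity the day after stimulation versus the day before".
- Section 8.3, Plans for Aim 7: Pearson's correlation between stimulation-induced changes in activity features. The second variable is not clearly stated. The analysis is labelled exploratory.

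Two further places speak of correlation without naming Pearson. Section 3.7 does so in general terms. The Synopsis outcome measure relates activity to a condition: "and stimulation versus no stimulation as well as gamma- versus control stimulation". The aim column of the Specific Aims table is similar: "To investigate whether there is a correlation between motor activity level and stimulation".

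The same table names mean differences as estimators for Aims 2, 4 and 6. It names none for Aim 7.

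**The concern.** Pearson's r suits Aims 5 and 8, which ask whether two different measures go together. Aim 7 asks whether one measure moves. A correlation between the day before and the day after shows whether active people stay active; it does not show whether activity rose or fell. A correlation between the gamma change and the control change shows whether people who changed more under one condition also changed more under the other, not whether the two conditions differ on average.

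Two misreadings follow. A significant r could be reported as an effect of stimulation when activity did not move. A clear rise or fall could go unreported because r is the same with or without it.

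**Working it through.** **Plan's own figure.** The documents give no effect size, power or precision for Aim 7. The only relevant figure is the sample size of 28 (Section 5.1, dz = 0.5, power 0.80, alpha 0.05). A paired t-test with dz = 0.5 needs 27 participants one-sided (power at 28 is 0.825) and 34 two-sided (power at 28 is 0.723). The present point does not depend on that difference.

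**Algebra.** For any constant c, Cov(X, Y + c) = Cov(X, Y) and SD(Y + c) = SD(Y), so r(X, Y + c) = r(X, Y). This is exact.

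**Illustration.** In one simulated set of 28 before/after pairs, adding 0, -10, +10 and +30 to every after value left r at 0.8074 each time. The mean change was 0.41, -9.59, 10.41 and 30.41, with paired p-values of 0.85, 9e-5, 3e-5 and 3e-14. In a second set, for gamma change against control change, a shift of 10 in the gamma changes left r at 0.448, while the mean difference went from -1.55 to 8.45.

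**Rejection rates.** Assumptions, since the documents give none: n = 28, bivariate normal, unit SD, shift 0 or 0.5 SD, two-sided 0.05, 40,000 simulated trials per setting. Rho is the correlation of the two days within a person. The label column correlates raw activity with a 0/1 condition, ignoring pairing (54 df).

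| Rho | r, no shift | r, shift | Label, no shift | Label, shift | Paired, shift |
|---|---|---|---|---|---|
| 0 | 5.2% | 5.1% | 5.1% | 44.8% | 43.4% |
| 0.25 | 25.5% | 25.2% | 2.4% | 44.2% | 54.8% |
| 0.5 | 79.8% | 79.8% | 0.7% | 43.0% | 72.4% |
| 0.7 | 99.2% | 99.3% | 0.1% | 41.9% | 90.7% |
| 0.8 | 100.0% | 100.0% | 0.0% | 41.2% | 98.1% |

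The paired test rejected in 4.7% to 5.0% of trials with no shift. As a check, the difference has SD sqrt(2(1 - rho)), so dz = 0.5/sqrt(2(1 - rho)). The noncentral t then gives paired power of 0.438, 0.549, 0.723, 0.909 and 0.981.

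**Precision of a mean change.** The 95% CI half-width is t(0.975, 27) x sqrt(2(1 - rho)/28), with t = 2.05. That is 0.548, 0.475, 0.388, 0.300 and 0.245 SD at the five values of rho.

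**Gamma change versus control change.** The same table applies if rho is the correlation of the two changes and the shift is 0.5 SD of a change. If all four days are equally correlated at rho within a person, the covariance of the two changes is rho - rho - rho + rho = 0. At a change correlation of 0, r is significant in about 5% of trials, and pairing gains nothing over the label (about 44% versus 45%). At -0.25, r is significant in 25%; the label has 45.9% power with a false-positive rate of 7.8%, and the paired test has 36.7% power.

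**The case against.** The strongest reply is that this is loose wording rather than a wrong estimator. The Synopsis outcome measure and the aim column of the table set activity against a condition, and a correlation with a 0/1 condition does respond to a mean difference. Section 4 says the design is meant "to allow not only an interindividual but also an intraindividual comparison of outcomes under both conditions", and Section 8.3 refers to the individual and group level. Section 3.7 and the aim column also word the aim itself as a correlation, so the conflict arises only against the Synopsis aim and the outcome column. This stands in part. On the condition-label reading the question is answered, and the criticism shrinks to the lost pairing. But that reading does not fit the estimator column, which makes the two days the correlated variables, or the Synopsis analysis plan, which correlates changes. Nothing in Section 4 or 8.3 supplies a summary statistic.

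The high rejection rates for r rest on assumed correlations and belong mainly to the before-versus-after reading. That stands: for gamma versus control they could be as low as the nominal 5%. The invariance of r needs no assumption.

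A mean change also has limits of its own. There is no unstimulated control period, and days before and after differ in scheduled lab visits, so the overall change mixes visit effects with stimulation. Wear ends at Visit 6, which starts between 8am and 12pm, so the second after window is short. These points stand. They bear on how windows are defined and how the overall change is read, and r would not escape them.

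**Conclusion.** The concern holds and is minor. As worded in the Synopsis analysis plan, the estimator and estimand columns of the Specific Aims table and Section 8.3, Pearson's r cannot show whether activity changed. That conclusion is algebraic. How misleading a reported r would be depends on the unknown within-person correlation: with no effect at all, r would be significant in about 5% of trials at 0, about 80% at 0.5 and nearly all at 0.7 or above, for n = 28 and two-sided 0.05. If the condition-label reading was intended, the aim is answered with less power when days are positively correlated (43% against 72% at 0.5 for a 0.5 SD shift).

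Aim 7 is exploratory, no trial decision depends on it, and the mean change can be computed from recordings already planned. The consequence is confined to how this aim is reported.

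**What to change.** Replace Pearson's r for Aim 7 in the Synopsis analysis plan, the Specific Aims table and Section 8.3, and align the Synopsis outcome measure and Section 3.7, with:

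- (a) the mean within-person change in activity, day after minus day before, with a 95% CI;
- (b) the within-person gamma-minus-control difference in that change, with a 95% CI, accounting for period by a paired difference or a mixed model.

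Define the before and after windows so that they fit the Visit 1 to Visit 6 wear period and cover the same clock hours in both periods. They may be shorter than 24 hours. Because of the visit-day differences, read (a) descriptively.

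As housekeeping, list the pre-stimulation occasions in the Table 1 actigraphy row. It shows N2A, D2A, N2B and D2B, which by the legend follow stimulation, although the thresholding rows use D2A for Visit 2 procedures.

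The cost is wording in five places and one table row. No new data, visit or participant is needed, and Aim 7 stays exploratory.
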